7.2. Subject Exclusion Criteria

Patients who meet any of the following criteria will not be randomized:

1. Total fasting (minimum of 10 hours) triglyceride ≥ 500 mg/dL (5.6 mmol/L) at Week -5 (Visit S1)

Note: TG may be repeated 1 time between Visits S1 and S2. For those patients who have a repeat TG, the repeat value will be used to determine eligibility.

2. Renal dysfunction or nephritic syndrome or a history of nephritis, including estimated glomerular filtration rate (eGFR) (using central laboratory determined Modification of Diet in Renal Disease [MDRD] formula) < 30 mL/min/1.73m² at Week -5 (Visit S1) (Levey 2006).

Note: At the discretion of the investigator, the screening period may be extended up to 4 weeks for a single repeat eGFR. For those patients who have a repeat eGFR, the repeat value should be obtained between visits S1 and S2 and will be used to determine eligibility.

3. Body mass index (BMI) ≥ 50 kg/m²
4. Recent (within 3 months prior to the screening visit [Week -5 (Visit S1)] or between screening and randomization visits) MI, unstable angina leading to hospitalization, uncontrolled, symptomatic cardiac arrhythmia (or medication for an arrhythmia that was started or dose changed within 3 months of screening), CABG, PCI, carotid surgery or stenting, cerebrovascular accident, transient ischemic attack (TIA), endovascular procedure or surgical intervention for peripheral vascular disease or plans to undergo a major surgical or interventional procedure (eg, PCI, CABG, carotid or peripheral revascularization). Patients with implantable pacemakers or automatic implantable cardioverter defibrillators may be considered if deemed by the Investigator to be stable for the previous 3 months.
5. Uncontrolled hypertension, defined as sitting systolic blood pressure (SBP) ≥ 160 mmHg and diastolic blood pressure (DBP) ≥ 100 mmHg after sitting quietly for 5 minutes

Note: If the initial blood pressure (BP) values meet or exceed the specified level, an additional BP assessment may be completed. If the systolic or the diastolic values continue to meet or exceed the threshold, the patient may not continue screening. However, at the discretion of the Investigator, the screening period (between Visits S1

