Muscle: Muscle events have been associated with statins ([Thompson 2003](#)) and other lipid-lowering therapies and are mentioned in the product information for those products. The exact mechanism in the development of muscle events is unclear. Bempedoic acid is a prodrug which needs to be converted by an acyl-CoA synthetase (ACS) to a coenzyme A (CoA) ester (ETC-1002-CoA). The specific ACS known to convert bempedoic acid into its active form is not present in skeletal muscle. This suggests that bempedoic acid may not lead to an increase in muscular side effects when given in conjunction with statins. Nonetheless, muscle symptoms through AE review, CK elevations, and symptoms of potential myopathy will be closely monitored. More detailed investigation will occur if results exceed 5 x ULN (see [Section 11.1.6.3.2](#)).

Diabetes and Hyperglycemia: New onset diabetes has been associated with the use of statins and is dose related. The product information for statins mentions hyperglycemia increased HbA_{1C} and increases in fasting glucose as potential adverse reactions. Hyperglycemia occurred in 10.8% (n = 10) of the placebo treated patients vs none of the bempedoic acid 180 mg treated patients in the Phase 2 program. Regardless, new onset diabetes through AE monitoring will be captured and summarized for this study and across all of the bempedoic acid studies. Clinical safety laboratories will also be evaluated during the studies including HbA_{1C}, and fasting glucose.

Renal: Nonclinical studies have demonstrated nephrotoxic effects on tubular cells of some lipid-modifying agents. In the Phase 2 program, creatinine elevations >25% over baseline occurred in 1 subject in the bempedoic acid 80 mg, 2 in the 180 mg, 1 in the 180 mg + ezetimibe, 1 in the 240 mg, and 3 in the 240 mg + baseline statin. In most cases, this elevation occurred at the end of the study and the values were not repeated and the events were not considered related. In 1 case, repeat values were obtained and the subject's creatinine was returning to baseline by Week 12. None exceeded a serum creatinine >1.8 mg/dL. No subjects withdrew due an AE of increased creatinine. In the Phase 3 program, repeat evaluation of creatinine will occur and patients exceeding protocol-specified values will be withdrawn from study medication (see [Section 11.1.6.3.2](#)). Patients will be monitored beyond the

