Cases of new onset of diabetes will be recorded as AEs and will be summarized using the appropriate SOC. These events will be summarized by severity and relationship to study drug for each treatment group. Glucose and HbA_{1C} will be monitored at baseline and at Weeks 12, 24, and 52, and be summarized.

Renal Safety

Baseline eGFR will be summarized by treatment group for actual value and for baseline eGFR categories. Shift tables of eGFR category from baseline over the study, will be provided by treatment group. Shift tables of urine protein (negative/positive) from baseline over the study, will be provided by treatment group. Values of CK over the study will be summarized by treatment group and by baseline eGFR category. Finally, muscle-related AEs will be summarized by treatment group and by baseline eGFR category.

Neurocognitive Events

Neurocognitive events will be identified and evaluated by routine safety monitoring of PE findings and AEs. Summarization of neurocognitive events will occur using prespecified MedDRA terms and will be performed by SOC, severity, and relationship to study drug for each treatment group.

Clinical Endpoints

Clinical endpoints using standardized definitions will be adjudicated by an independent blinded expert CEC for all ongoing Phase 3 studies in the bempedoic acid program. Investigator-reported clinical endpoints and adjudicated clinical endpoints will be summarized by event type and treatment group. Additional details regarding the clinical endpoints and their definitions will be included in CEC Charter.

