11. DEMOGRAPHIC AND OTHER BASELINE CHARACTERISTICS

Demographic data and other baseline characteristics will be summarized by treatment group for the FAS.

No statistical testing will be carried out for demographic or other baseline characteristics.

The following demographic and other baseline characteristics will be reported for this study:

- Age (years) - calculated relative to date of randomization
- Age category (<65 years vs. ≥65 years and < 75 years vs. ≥75 years)
- Gender
- Race
- Ethnicity
- Region (US vs. Canada vs. EU)
- Stratification factor
- CV risk (ASCVD only; HeFH (with or without ASCVD))
- Baseline statin intensity (high intensity; moderate intensity; low intensity)
- Weight (kg)

Statistical Analysis Plan

- Height (cm)
- BMI (kg/m²)
- BMI category (< 25 vs. 25 - < 30 vs. ≥ 30 kg/ m2)
- Baseline Laboratory Results (Total Cholesterol, LDL-C, HDL-C, Triglycerides, Non-HDL-C, Apolipoprotein B, and hsCRP)
- Baseline LDL-C category (<130 mg/dL, ≥130 and < 160 mg/dL, or ≥160 mg/dL)
- Baseline eGFR (normal: ≥90 mL/min/1.73m²; mild Renal Impairment: 60-89 mL/min/1.73m²; moderate Renal Impairment: 30-59 mL/min/1.73m², and severe Renal Impairment (15-29 mL/min/1.73m²)
- History of diabetes (Yes vs. No)
- History of hypertension (Yes vs. No)
- Baseline Vital Signs (systolic blood pressure (SBP) and diastolic blood pressure (DBP))
- Alcohol consumption (Non-Drinker, Former Drinker, or Current Drinker)
- Tobacco use (Never Used, Former User, or Current User)

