18.4. SAFETY LABORATORY EVALUATIONS

Results from the central laboratory will be included in the reporting of this study for Hematology, Blood Chemistry, Lipids, Coagulation, HbA1C, hsCRP and Urinalysis. A list of laboratory assessments to be included in the outputs is included in Protocol, Section 11.1.6.1.

Presentations will use SI Units and conventional units.

Quantitative laboratory measurements reported as “< X”, i.e. below the lower limit of quantification (BLQ), or “> X”, i.e. above the upper limit of quantification (ULQ), will be converted to X for the purpose of quantitative summaries, but will be presented as recorded, i.e. as “< X” or “> X” in the listings.

The formula to calculate eGFR is: $eGFR = 186 \times (\text{Creatinine} / 88.4)^{-1.154} \times (\text{Age})^{-0.203} \times (0.742 \text{ if female}) \times (1.210 \text{ if black})$, where creatinine is in mmol/L.

Summaries for all lab results, including unscheduled visit values, will be included for below analyses:
 Observed and change/percent change from baseline by visit (for quantitative measurements).

Shift from baseline by visit according to normal ranges.

Shift from baseline according to normal ranges for HbA1c and glucose by history of diabetes and visit.
 eGFR and values of CK will be summarized by treatment group and by baseline eGFR categories (low, normal, high).

Potential Hy’s law cases (>3 × ULN for either ALT or AST AND Total Bilirubin >2 × ULN in the setting of no known other cause) will be tabulated and listed.

Laboratory abnormalities in parameters of interest

- ALT or AST (> 3x ULN , >5xULN)
- TB (>2x ULN)
- CK (> 5x ULN) and (>10x ULN)
- Fasting Blood Glucose (≤50 mg/dL, ≥126 mg/dL) by history of diabetes
- HbA1c (≥6.5%) by history of diabetes
- Creatinine (change from baseline for >1 mg/dL)
- eGFR (< 15 mL/min/1.73m², 15 –< 30 mL/min/1.73m²)
- Hgb (decrease from baseline for ≥2 g/dL)
- Hgb (<8 g/dL)

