18.4.1. LABORATORY REFERENCE RANGES AND MARKEDLY ABNORMAL CRITERIA

Quantitative laboratory measurements will be compared with the relevant laboratory reference ranges in SI units and categorized as:

Low: Below the lower limit of the laboratory reference range.

Normal: Within the laboratory reference range (upper and lower limit included).

High: Above the upper limit of the laboratory reference range.

In addition to the high and low quantitative laboratory assignments, Hy's law criteria ($\geq 3 \times \text{ULN}$ for either ALT or AST, with accompanying total bilirubin $> 2 \times \text{ULN}$ in the absence of other known causes) will be used to identify potential Hy's law cases.

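### The eGFR formula in SAP 18.4 divides creatinine by 88.4 but gives its unit as mmol/L; applied as printed, every eGFR is about 2,900 times too high

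*SAP*

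**What the plan says.** SAP 18.4 introduces its derivation with "The formula to calculate eGFR is" and then sets eGFR = 186 × (creatinine/88.4)^−1.154 × age^−0.203, times 0.742 for women and 1.210 for black patients. It closes with the unit instruction: "where creatinine is in mmol/L". The SAP contains no other eGFR derivation.

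The results are read against cut-offs on the usual clinical scale:

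- SAP 18.4 flags eGFR below 15 and from 15 to below 30 mL/min/1.73 m².
- SAP 11 classes baseline eGFR as normal (90 or more), mild (60–89), moderate ("moderate Renal Impairment: 30-59") or severe (15–29).
- Protocol 12.8, under Renal Safety, promises: "Shift tables of eGFR category from baseline over the study, will be provided by treatment group".

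Elsewhere the documents give creatinine in mg/dL. The SAP flag reads "Creatinine (change from baseline for >1 mg/dL", and Protocol 11.4 says of the Phase 2 subjects with creatinine elevations: "None exceeded a serum creatinine >1.8 mg/dL".

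**The concern.** The divisor and the unit sit in the same formula statement and disagree by a factor of 1,000. The number 88.4 converts creatinine from micromol/L to mg/dL, the scale on which the coefficient 186 gives values that fit the SAP's own categories. A programmer who follows the printed unit enters values 1,000 times too small, and the negative exponent turns that into a very large overestimate of kidney function.

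Renal events are adverse events of special interest in this trial (Protocol 11.4), and patients can enter with eGFR as low as 30 (Protocol 7.2). Applied literally, the formula would leave both eGFR abnormality flags empty in both arms and put every patient in the normal baseline category. The laboratory-abnormality table for parameters of interest is also among the Data Monitoring Committee outputs in SAP Appendix 3. Protocol 12.1 lets the SAP override the protocol on analysis and appends it to the study report, so the printed formula is the derivation of record.

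**Working it through.** The documents state no eGFR result to reproduce, so the check evaluates the formula under both units.

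**Inputs.** Divisor 88.4, exponents −1.154 and −0.203, and coefficient 186 come from SAP 18.4. The cut-offs 15 and 30 are in SAP 18.4, and 90 is in SAP 11. The molar mass of creatinine, 113.12 g/mol, is not in the documents and is an assumption.

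**Step 1: which unit fits 88.4.** 1 mg/dL = 10 mg/L, and 10/113.12 = 0.0884 mmol/L = 88.4 micromol/L. The exact molar mass does not matter here. Any value from 110 to 116 g/mol gives 10,000/110 = 90.9 down to 10,000/116 = 86.2 micromol/L, so the mismatch with mmol/L stays at about 1,000-fold.

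**Step 2: size of the error.** Entering the same creatinine in mmol/L instead of micromol/L divides it by 1,000. The ratio of the two results is (1/1000)^−1.154 = 1000^1.154 = 2,897. Age, sex, race and the creatinine level cancel.

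**Step 3: worked values.** For a non-black man aged 65, 186 × 65^−0.203 = 79.706.

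| Creatinine (mg/dL) | eGFR, micromol/L entered | eGFR, mmol/L entered |
|---|---|---|
| 1.0 | 79.7 | 230,936 |
| 1.8 | 40.4 | 117,194 |
| 4.0 | 16.1 | 46,635 |

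The 1.8 mg/dL row takes its value from Protocol 11.4. That sentence describes only the subjects with creatinine elevations, so it is an illustrative value and not a maximum for all of Phase 2.

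**Step 4: creatinine needed to reach each cut-off t.** With micromol/L the threshold is (79.706/t)^(1/1.154) mg/dL. With the printed unit it is (79.706 × 2,897.3/t)^(1/1.154) mg/dL.

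| eGFR below | micromol/L entered | mmol/L entered |
|---|---|---|
| 90 | above 0.90 mg/dL | above 900 mg/dL |
| 30 | above 2.33 mg/dL | above 2,332 mg/dL |
| 15 | above 4.25 mg/dL | above 4,252 mg/dL |

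For a non-black woman aged 80, the printed unit gives thresholds of 670, 1,736 and 3,165 mg/dL. None of these is physiologically possible. With micromol/L the worked values fall inside the SAP's own categories, so micromol/L is the only workable reading.

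**The case against.** **The printed unit may not be what the SAP says.** A micro sign in a PDF can be misread as the letter m, and the whole point rests on that character. The Greek letter survives in the exposure units of Protocol 4.2.2 and in the hypotheses of SAP 17.1.2, but those are typeset expressions. The SAP has no micro-unit in ordinary text for comparison. This doubt stands, and only the source PDF can settle it.

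**Nobody would miss an eGFR of 230,936.** The cut-offs in SAP 11 and 18.4 fix the expected scale, and screening gives an independent comparison, since eligibility eGFR is obtained "using central laboratory determined Modification of Diet in Renal Disease [MDRD] formula" (Protocol 7.2). An error this large could not quietly bias a comparison between arms. This also stands. It lowers the chance of wrong tables but does not make the written derivation correct.

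**The reach is limited.** Efficacy, eligibility, the on-study eGFR withdrawal rule, the creatinine-rise flag and the renal adverse-event terms do not use the formula. The effect on the protocol's shift tables is conditional: SAP 18.4 plans shifts by normal range and specifies no eGFR-category shift table. They would show no decline only if they were built on the SAP 11 categories with the literal formula.

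**Conclusion.** The concern holds as the text stands. The unit printed in SAP 18.4 is inconsistent with the divisor beside it, and following it inflates every eGFR by 2,897. The direct consequences would be two empty abnormality flags and no patient in any reduced baseline category. The conclusion uses the molar mass of creatinine as an outside constant, but the SAP's own eGFR categories point to the same reading without it. Two things remain open: whether the source PDF really reads mmol/L, and whether the program followed it.

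**What to change.** 1. Check the source PDF of SAP 18.4.
2. If it reads mmol/L, change the unit to micromol/L. Keeping mmol/L and dividing by 0.0884 would be equivalent.
3. Confirm the creatinine unit used in the eGFR program. The SAP addendum of December 2018 says the planned analyses are complete, so this would be a documented correction plus that confirmation.

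The cost is a one-word unit correction and one check of the derivation program, with no new data or analyses.

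Optional and separate from the unit error: SAP 18.4 also summarizes eGFR and CK by low, normal and high baseline eGFR. SAP 18.4.1 ties those labels to the laboratory reference range ("Low: Below the lower limit of the laboratory reference range"). Using the SAP 11 renal categories there would give all baseline-eGFR tables one set of categories.

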APPENDIX 1. SCHEDULE OF EVENTS (SUBJECT VISIT SCHEDULE)

	Screen	Run-in		Treatment						
Visit	S1 ^{1,2}	S2	S3	T1	T2	T3/phone	T4	T5	T6/phone	T7/EOS ³
Week	Wk -5	Wk -4	Wk -1	Wk 0	Wk 4	Wk 8	Wk 12	Wk 24	Wk 36	Wk 52
Procedure	Day -35±7	Day -28±3	Day -7±3	Day 1	Day 29±3	Day 57±3	Day 85±3	Day 168±7	Day 252±7	Day 365 ±7
Informed Consent	X									
Enrollment Criteria	X									
Demographics	X									
Medical History	X									
HeFH Status Determination	X									
Concomitant Medications	X	X	X	X	X	X	X	X	X	X
Adverse Event Recording		X	X	X	X	X	X	X	X	X
Physical Exam				X						X
Weight ⁴	X			X	X		X	X		X
Height/BMI	X									
12-Lead ECG ⁵				X						X
Vital Signs ⁶	X	X	X	X	X		X	X		X
Serology ⁷	X									
Serum Pregnancy and/or FSH ⁸	X									
Urine Pregnancy Test ⁸				X						
TSH	X									
Clinical Safety Labs ⁹	X			X	X		X	X		X
Basic Fasting Lipids ¹⁰	X		X	X	X		X	X		X
HbA _{1c}	X			X			X	X		X
apoB				X			X	X		X
hs-CRP				X			X	X		X
Diet and exercise counseling ¹¹	X	X	X	X	X	X	X	X	X	X
Plasma PK								X		X
Establish Patient Eligibility				X						
Randomization				X						
IWRS Contact	X	X		X			X	X		X ¹²
Single-Blind Drug Dispensing		X								
Double-blind Drug Dispensing ¹³				X			X	X		
Drug Return/Compliance			X	X	X		X	X		X
Schedule next visit	X	X	X	X	X	X	X	X	X	

NOTE: For patients who withdraw from IMP treatment, they will continue to have visits according to the protocol schedule. Safety assessments should include clinical safety and basic lipid laboratories (except for apoB and hs-CRP), adverse events, PE, vital signs, and ECGs. For patients who withdraw from IMP treatment, but refuse to come to the clinic for assessments, assessments will take place by phone. The telephone contacts will occur according the protocol schedule with information regarding current health status and to collect information on AEs (eg, recent procedures, hospitalizations, and if the patient has died, the cause of death).

- ¹ An optional visit between Visits S1 and S2 may be completed if patient fails to meet TG entry criterion. If this optional basic fasting (minimum of 10 hours) lipid value visit is completed, the repeat lipid value will be used to determine eligibility.

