5.1. SAFETY ANALYSIS SET [SAF]

The Safety Analysis Set (SAF), used for all of the safety summaries, is defined as all randomized patients who received at least 1 dose of double-blind study medication. Patients in the SAF will be included in the treatment group that they actually received, regardless of their randomized treatment.

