6.4. VISIT WINDOWING

Protocol-defined assessments will be “slotted” to study weeks based on collection date and applying the rules summarized in the following table. If there is more than one scheduled visit in a visit window, the visit closest to the target date will be used. If there is a tie between the numbers of days from the target date, the visit after the target date will be used. Unscheduled visits that fall within the protocol-defined visit windows will be summarized in the by-visit analyses if there is no scheduled visit available. If there is more than one unscheduled visit within the protocol-defined visit window and no scheduled visit available, the unscheduled visit closest to the scheduled visit date will be used. If there is a tie between the numbers of days from the target date, the visit after the target date will be used.

However, exposure data obtained from the drug accountability and administration CRF will be summarized and listed according to nominal visit information.

Analysis Visit	S1	S2	S3	T1	T2	T3	T4	T5	T6	T7
Study Week	-5	-4	-1	week 0	4	8	12	24	36	52/EOS
Target Study Day	-35	-28	-7	1	29	57	85	168	252	365
Analysis Visit Windows	$[-\infty, -32]$	$[-31, -18]$	$[-17, -1]$	$[1, 1]$	$[2, 43]$	$[44, 71]$	$[72, 127]$	$[128, 211]$	$[212, 309]$	$[310, \infty]$

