17.2.3.3. On-treatment Analysis

To explore the impact to efficacy from patient discontinue study medication, an on-treatment analysis will also be conducted for primary and key secondary endpoints using data collected from the on-treatment period, i.e. lab test date \leq of last dose of double-blind IMP+7 days. On-treatment analysis will be based on FAS. There will be no imputation for missing data.

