18.1. ADVERSE EVENTS

Adverse Events (AEs) will be coded using MedDRA, Version 20.1.

Treatment emergent adverse events (TEAEs) are defined as AEs that started or worsened in severity after the first dose of double-blind study medication and prior to the last date of study medication + 30 days. AEs that occurred on day 1 will be only be determined as TEAE if the site indicated it occurred after first dose on the AE CRF.

See [Appendix 2](#) for handling of partial dates for AEs. In the case where it is not possible to define an AE as treatment emergent or not, the AE will be classified by the worst case scenario, i.e. treatment emergent.

An overall summary of number of patients within each of the categories described in the sub-section below, will be provided as specified in the templates. Listings will include TEAEs and Non-TEAEs.

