18.6. VITAL SIGNS

The following Vital Signs measurements will be reported for this study:

- Sitting Systolic Blood Pressure (mmHg)
- Sitting Diastolic Blood Pressure (mmHg)
- Sitting Heart Rate (bpm)
- Weight (kg)
- Height (cm) (at Screening only)
- BMI (kg/m²) (calculated automatically by the EDC system)

The following summaries will be provided for vital signs data:

- Observed and change from baseline by visit

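### Safety laboratory and vital-sign summaries have no cut-off after last dose, so off-drug samples enter the later visits; an on-treatment version should be added beside them

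*SAP*

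**What the plan says.** **Data that enter the summaries.** SAP 18.4 says: "Summaries for all lab results, including unscheduled visit values, will be included for below analyses". The analyses that follow are observed values and changes by visit, shifts from baseline, and counts of abnormalities in parameters of interest. SAP 18.6 plans "Observed and change from baseline by visit" for vital signs.

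**Patients and windows.** The Safety Analysis Set (SAP 5.1) "is defined as all randomized patients who received at least 1 dose of double-blind study medication". It selects patients and does not limit observation time. SAP 6.4 assigns assessments "to study weeks based on collection date and applying the rules summarized in the following table". Week 4 covers days 2 to 43, and Week 52 runs from day 310 with no upper limit.

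**After stopping.** The note in Protocol Appendix 1 says: "For patients who withdraw from IMP treatment, they will continue to have visits according to the protocol schedule". It lists safety laboratories and vital signs among the assessments. Patients who refuse clinic visits are followed by phone and give no samples.

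**Limits set elsewhere.** SAP 18.1 counts an adverse event as treatment-emergent if it started or worsened "after the first dose of double-blind study medication and prior to the last date of study medication + 30 days". In SAP 17.2.3.3, "an on-treatment analysis will also be conducted for primary and key secondary endpoints using data collected from the on-treatment period", defined there as up to 7 days after last dose. No such limit or sensitivity table is planned for laboratories or vital signs.

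**The concern.** Long-term (52-week) safety is a stated objective (Protocol 5.1.3), and safety laboratories and vital signs are named safety endpoints (5.2.4). A reader of the Week 4, 12, 24 and 52 columns will ask whether a change on drug persists, grows or wanes. If later columns contain more patients who are off drug, a change that reverses on stopping looks smaller at those visits even when it is constant in patients still taking the drug. The planned tables do not let a reader separate the two explanations.

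Stopping is also linked to these measurements. Protocol 11.1.6.3.1 to 11.1.6.3.4 call for withdrawal from study drug at certain liver enzyme, eGFR, hemoglobin and CK results, while asking the patient to stay in follow-up. Patients with the largest laboratory effects may then contribute recovered values to later active-arm means.

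Finally, the two safety displays cover different time at risk. A laboratory abnormality found months after last dose is counted under SAP 18.4, but an adverse event starting on the same day falls outside the TEAE tables.

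**Working it through.** The plan states no off-drug share, so there is no figure of its own to reproduce.

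**1. Does anything in the SAP remove off-drug samples?** The analysis set selects by one dose taken. The windows use collection date. SAP 6.3 and 6.4 decide which value represents a visit, not whether the patient was on drug. SAP 6.4 uses an unscheduled value only when no scheduled visit is available, so a by-visit table does not hold literally every sample; that rule does not depend on last dose either. Nothing removes them.

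**2. How large could the share be?** Assumed, because neither document gives these rates: d = proportion stopping by Week 52, 5-30%; r = proportion of those who still attend clinic, 25-100%. Stopping has a constant hazard, and all patients on drug attend.

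- Stopped by week t: F(t) = 1 - (1 - d)^(t/52)
- Off-drug share: S(t) = rF / (1 - F + rF)

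Example at Week 52 with d = 0.20 and r = 0.80: F = 0.20, so S = 0.16 / (0.80 + 0.16) = 16.7%. That is 500 x 0.20 x 0.80 = 80 active-arm patients.

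| d | r | Week 4 | Week 12 | Week 24 | Week 52 |
|---|---|---|---|---|---|
| 5% | 25% | 0.1% | 0.3% | 0.6% | 1.3% |
| 10% | 50% | 0.4% | 1.2% | 2.4% | 5.3% |
| 10% | 80% | 0.6% | 1.9% | 3.8% | 8.2% |
| 20% | 80% | 1.4% | 4.1% | 8.0% | 16.7% |
| 30% | 80% | 2.2% | 6.4% | 12.5% | 25.5% |
| 30% | 100% | 2.7% | 7.9% | 15.2% | 30.0% |

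The formula counts everyone who has stopped, including those within 7 days of last dose, so it slightly overstates the share beyond 7 days.

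**3. Early stopping.** If a quarter of all stops occur by Week 4, then F(4) = 0.25d. With d = 10-30% and r = 50-100%, the Week 4 share is 1.3% (0.0125 / 0.9875) to 7.5% (0.075 / 1). The rise from Week 4 to Week 52 is then less steep.

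**4. Effect on a mean.** For a change that reverses fully off drug, the displayed mean is the on-drug mean x (1 - S). At Week 52 that is 98.7% to 70% of its on-drug size over the assumed range.

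**5. Drug remaining 7 days after last dose.** Protocol 4.2.3 gives half-lives of 15-27 h for the parent and 20-33 h for the metabolite. With first-order decay, the fraction left is 0.5^(168/half-life): 0.04-1.3% for the parent and 0.3-2.9% for the metabolite. This shows washout of drug, not recovery of a laboratory value.

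**The case against.** **All-data tables follow the plan's own logic.** Protocol 12.8 summarises laboratories at each postbaseline time point. The main efficacy analysis uses patients regardless of treatment received, and on-treatment efficacy is only a sensitivity analysis. The safety tables are descriptive, with no between-group comparison unless specified (SAP 18). This stands. A reader might infer that the on-treatment table should become the main one, but the documents do not support that.

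**An on-treatment table has its own selection.** Patients withdrawn for a laboratory result drop out of its later visits, so its Week 24 and Week 52 means lean toward those who tolerated the drug. That can also look like waning. This stands too, and it is the reason to show both versions.

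**Reversibility is documented only in part.** The protocol reports reversible liver and kidney changes in animals (4.2.2) and liver tests that improved off drug (11.4). It reports none for uric acid, hemoglobin, CK or vital signs. Section 11.1.6.3.3 requires weekly hemoglobin checks after withdrawal for a low value, so recovery within 7 days cannot be assumed. A reader might infer that drug effects must fade by construction. What follows is narrower: dilution in proportion to the off-drug share, for effects that reverse.

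**Abnormality counts do not simply mask.** Extra follow-up can only add patients to a count of those ever abnormal. Percentages by visit and differences between arms can move in either direction.

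**The DMC tables are known only by title.** SAP Appendix 3 lists 14.3.2.8 and 14.3.2.9 without a cut-off, but their templates are not in the file. What they contain cannot be confirmed.

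**Conclusion.** The gap is real. The observation window for laboratories and vital signs has no end relative to last dose, off-drug samples are collected by design, and the SAP sets such limits elsewhere.

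The size is not known. About 1-30% off-drug samples at Week 52 rests on the assumed ranges of stopping and attendance. A reader might take a narrower figure such as 8-25%, with almost none at Week 4, as following from the plan. It does not. At 80% attendance that Week 52 range needs about 10-29% to stop, and early stopping would raise the Week 4 share. The share can also fall between visits, since Protocol 10.3.1 permits restarts and attendance may lapse. It will differ by parameter, because HbA1c is not named in the post-withdrawal list.

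No hypothesis test is affected. This is a worthwhile, inexpensive addition to descriptive tables that address the 52-week safety objective.

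**What to change.** Keep the all-data tables in SAP 18.4 and 18.6 as planned. Add an on-treatment version, with the cut-off stated for each table type:

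- By-visit summaries (laboratories and vital signs) and laboratory shift tables: samples up to last dose + 7 days, as in SAP 17.2.3.3.
- Laboratory abnormality counts: samples up to last dose + 30 days, to match the TEAE period in SAP 18.1.
- In each by-visit table: the number of on-drug and off-drug samples per visit and arm.

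Make the same addition to DMC tables 14.3.2.8 and 14.3.2.9. The SAP addendum says the planned analysis is complete, so tables produced now should be labelled supplementary.

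The cost is one date filter per table type and a few extra tables; no data are lost. A note should say that the later on-treatment means are selected toward patients who tolerated the drug and are to be read beside the all-data version, not in its place.
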